5.6 Compliance

Compliance with study treatment will be presented as the number and proportion of patients who received the two IMP injections. A listing of treatment compliance will be provided.

5.7 Efficacy

5.7.1 General Considerations

The primary efficacy analysis will be performed on the ITT population. Supportive analysis of the primary efficacy endpoint will be based on the mITT and the PPS population.

The secondary efficacy analyses will be based on the ITT population.

A listing of all efficacy data (raw and derived) should be provided (see listing detail conventions in Appendix A4). Descriptive statistics will be provided for all endpoints.

5.7.1.1 Significance Testing and Estimations

For the primary efficacy endpoint, the summary statistics of number and percentage of participants and the exact two-sided 95% confidence interval (CI) for a binomial proportion will be computed by SAS® using the exact binomial distributions on the ITT (primary population of analysis) population.

For secondary efficacy endpoints related to a change at Months 3, 6, 9 and 12 compared to baseline, the descriptive summary statistics (n, mean, SD, median, minimum, maximum) will be calculated on the ITT. Exact two-sided 95% CIs will also be constructed for all secondary endpoints expressed as percentages.

5.7.1.2 *Handling of Dropouts and Missing Data*

Diligent attempts will be made to limit the amount of missing data and to follow-up all treated participants to collect the primary and secondary efficacy endpoints for the statistical analysis.

A Non-responder imputation (NRI) method will be used for all definition of response, for instance, participants who discontinue before evaluation of the endpoint (Month 3, Month 6, Month 9 and Month 12) will be declared non-responder.

5.7.1.3 *Statistical/Analytical Issues*

Adjustments for Covariates

No covariate adjustment analysis is planned in this study.

Interim Analyses and Data Monitoring

No interim analysis will be performed.

Multicentre Studies

No by-centre displays or adjustments for centre are planned for this study.

Multiple Comparisons/Multiplicity

No multiple testing will be performed in this study since this is a single arm study.

5.7.2 *Analysis of Primary Efficacy Endpoint*

5.7.2.1 *Endpoint*

LH suppression: defined as a peak LH ≤ 5 IU/L after intravenous (i.v.) gonadotropin-releasing hormone (GnRH) stimulation in Chinese children with central precocious puberty (CPP).

The primary endpoint is proportion of children with LH suppression at Month 6.

5.7.2.2 *Primary Analysis*

For the primary efficacy endpoint, the summary statistics of number and percentage of participants and the exact two-sided 95% CI for a binomial proportion will be computed by SAS® using the exact binomial distributions on the ITT.

The SAS code to be used could be presented in Appendix A1.

A listing will be provided including all participants with missing values for the primary endpoint. For these participants, the listing will provide all observed data related to the primary endpoint i.e. all measurements recorded prior to the missing value, any measurements recorded after the missing value, important baseline characteristics, the reason and timing for study discontinuation. The listing will also provide the imputed value(s) (if applicable) used in the primary analysis and any sensitivity analyses.

5.7.2.3 *Sensitivity Analysis*

Sensitivity analysis of the primary efficacy endpoint will be conducted with the same statistical method based on the mITT and the PPS population.

5.7.2.4 *Supplementary Analysis*

No supplementary analyses will be performed.

5.7.2.5 *Subgroup Analysis*

No subgroup analyses will be performed.

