1.3 Schedule of Activities

If the COVID-19 pandemic prevents participants from coming to the site, participants can have their study visit assessments performed remotely as judged appropriate by the investigator. This must be discussed with the sponsor before being implemented. In such a case, the investigator will perform a telemedicine visit and will make every effort, where applicable, to contact the participant's general practitioner or specialist physician to ensure all important medical information and safety event(s) occurring since the last visit are collected. Guidance on how to collect protocol-planned assessments will be provided to the investigator in a separate document. Such document will be filed in the trial master file. Independent ethics committees (IECs)/institutional review boards (IRBs) will be notified of the changes as applicable locally. Of note, as the adapted visit deviates from the regular protocol plan, the changes will be recorded as protocol deviations related to COVID-19.

Table 2 Schedule of Activities

Procedures [a]	Screening Visit		Month 3	Month 6	Month 9	Month 12
	Day -28 to Day -1 Prior to Treatment	Day 1	Day 85	Day 169	Day 253	Day 337 (EOS/Early Withdrawal) [u]
Visit window (days)			±3 days	±3 days	±3 days	+7 days
Informed consent /assent [b]	X					
Inclusion and exclusion criteria [c, d]	X	X				
Demography	X					
Medical and surgical history	X					
PK samples[e]		X	X	X		X
Basal LH and FSH [f]	X		X	X	X	X
GnRH test with LH and FSH [g]	X		X	X		X
Oestradiol or testosterone [h]	X		X	X	X	X
Pubertal Stage (Tanner method) [i]	X			X		X
Auxological parameters [j]	X		X	X	X[v]	X
Bone age [k] and chronological age	X			X		X
Gonad development [l]	X			X		X
Body weight [m]	X	X	X	X	X	X
Adverse events [n]	X	X	X	X	X	X
Pregnancy test [o]		X				X
Clinical laboratory tests [p]	X	X[w]	X	X	X	X
Physical examination and vital signs [q]	X	X	X	X	X	X

CONFIDENTIAL

PROTOCOL VERSION 2.0: 29 APRIL 2022

PAGE 20/63

Procedures [a]	Screening Visit		Month 3	Month 6	Month 9	Month 12
Prior and concomitant medications [r]	X	X	X	X	X	X
Study drug administration [s]		X		X		
Local tolerability [t]		X		X		

BMI=body mass index; CPP=central precocious puberty, eCRF=electronic case report form, EOS=End of Study; FSH=follicle-stimulating hormone; GnRH=gonadotropin-releasing hormone; IEC=Independent Ethics Committee; IRB=Institutional Review Board; LH=luteinising hormone; MRI=magnetic resonance imaging, PK=pharmacokinetic.

Footnotes to Schedule of Assessments

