10.6 Appendix 7: Temporary Measures and Procedures Related to COVID-19 Pandemic

This appendix serves as notification of the temporary measures put in place for the conduct of the study during the COVID-19 pandemic and until such time as the situation resolves, at which point the protocol assessments will return to those specified in the current approved protocol effective at that time. The timing of when the pandemic is declared over may vary on a country by country basis as well as between sites in the same country, and as such the temporary measures may remain in place for differing periods of time per country/site. Investigators will determine the feasibility of starting or continuing study treatment on a patient by patient basis, depending on the ability to conduct safety monitoring and providing patients an adequate supply of study treatment, in accordance with local requirements.

Any temporary measure will be reported as a protocol deviation related to COVID-19.

Withdrawal from Study

Participants who are suspected or confirmed to have COVID-19 infection after enrolment will withdraw from the study (see also Section 7.1.2 for temporary withdrawal).

Telemedicine Visit

If the COVID-19 pandemic prevents participants from coming to the site for the Month 9 visit, the investigator will perform a telemedicine visit to collect all important medical information and safety event(s) occurring since the last visit. Besides the Month 9 visit, the participants may delay other visits no more than 2 weeks and preferably within 1 week or be withdrawn from the study as appropriate, as judged by the investigator and agreed with the sponsor.

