2.3 Sample Size Determination and Power

The sample size of this study is estimated based on following assumptions according to global pivotal study DEBIO 8206-CPP-301 [Klein 2016].

- Expected outcome for the proportion of children with a suppressed LH response to the GnRH stimulation test (stimulated peak serum LH ≤ 5 IU/L) at Month 6 is 93%;
- Null proportion is 80%;
- An exact binomial test of a proportion with a one-sided nominal significance level of 0.025 and power =85%;
- Expected common dropout rate =5%.

Under these assumptions, approximately 66 participants (Power Analysis and Sample Size

(PASS) software)) are planned to be enrolled into the study to ensure there are 62 treated participants to confirm the efficacy of the triptorelin 6-month formulation by the proportion of children with a suppressed LH response to the GnRH stimulation test at Month 6.

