5.1.2 Descriptive Statistics

All raw and derived variables will be listed and described using summary statistics. For categorical variables, summary statistics will be displayed using descriptive statistics by frequency count and percentages by category. The missing category will be presented if there is at least one missing category for at least one gender group. Except otherwise specified, participants with missing data will be included in the calculation of percentages. For quantitative variables, summary statistics will be displayed using descriptive statistics by number of observations, mean, SD, median, minimum and maximum. Missing data will be displayed.

5.1.3 *Baseline Value*

Unless otherwise specified, baseline is defined as the last non-missing measurement taken prior to first IMP administration (including unscheduled assessments). If the assessment time and/or IMP administration time is not collected, the assessment performed on the same day as the first IMP administration will be considered as baseline.

5.1.4 *Reference Start Date and Study Day*

Reference start date is defined as the day of the first IMP administration.

The day of the first IMP administration will be Day 1. Study day will be calculated as:

- The difference between the event date and the reference date plus one day, if the event is on or after the reference date.
- The difference between the event date and the reference date, if the date of event is prior to the reference date.

Study day will appear in any listings where an assessment date or event date appears.

In case of partial or missing event date, study day will appear missing while any associated durations will be presented based on the imputations described in appendix A2.

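### If a COVID-19 telemedicine visit leaves no centrally assayed Month 9 sample, the SAP's non-responder rule as worded counts a child still in the study as not suppressed on sex steroids

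*SAP*

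**What the plan says.** **The visit.** Protocol 10.6 (Appendix 7): "If the COVID-19 pandemic prevents participants from coming to the site for the Month 9 visit, the investigator will perform a telemedicine visit". The stated purpose is to gather clinical and safety information since the previous visit; sampling is not mentioned. Under the same appendix the other visits may be delayed by up to two weeks, or the child withdrawn. Protocol 1.3 is broader: "participants can have their study visit assessments performed remotely as judged appropriate by the investigator". It leaves the method of collecting planned assessments to a separate document that is not part of the protocol or SAP.

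**The endpoint.** The schedule of activities places oestradiol or testosterone at Month 9, and SAP Table 1 lists the proportion at pre-pubertal level at Months 3, 6, 9 and 12. It is the only responder endpoint at Month 9. Protocol 10.2 restricts the hormone analyses to central laboratory results.

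**The missing-data rules.** SAP 5.7.1.2: "A Non-responder imputation (NRI) method will be used for all definition of response". The one example given is a participant who discontinues before the assessment, with Months 3, 6, 9 and 12 named. SAP 5.1.2 adds that, unless specified otherwise, "participants with missing data will be included in the calculation of percentages". SAP 5.7.1 analyses secondary efficacy on the ITT set (at least one dose), and SAP 5.7.3.3 plans no sensitivity analysis for secondary endpoints.

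**The concern.** Counting a child who leaves the study as a non-responder is a defensible conservative convention, because leaving may be related to failure. A child whose Month 9 site visit was replaced because of the pandemic is in a different position: still in the study, and lacking a result for a reason that need not have anything to do with hormone levels. The SAP does not separate the two cases, so its general wording sweeps in the second.

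At stake is the reading of one time point. Month 9 (Day 253) is the only hormone reading between the second injection at Month 6 (Day 169) and the final visit (Day 337). A lower Month 9 proportion, read alone, could be taken as weaker suppression in that interval when part or all of it merely counts missing samples. No other planned analysis of this proportion would show the difference.

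**Working it through.** **The plan's own figure, to fix N.** Inputs from SAP 2.3: null proportion 80%, expected proportion 93%, one-sided exact binomial test at 0.025, power 85%, dropout 5%. With n = 62 the test needs at least 56 responders; exact type I error is 0.0238 and power 0.858. Enrolment is 62 / 0.95 = 65.3, rounded up to 66. The planned 62 and 66 reproduce. The point does not depend on this test; it supplies only the two values of N.

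**Quantities not in the documents (assumptions).** k, the number of continuing children with no Month 9 central sample after a telemedicine visit, and p, the true Month 9 sex steroid suppression rate.

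**Formulas.** With x children observed to be suppressed:
- Rate under the SAP wording = x / N.
- Observed-case rate = x / (N − k).
- Loss per truly suppressed child affected = 1 / N: 1/66 = 1.5 points, 1/62 = 1.6 points.
- Expected shortfall = p × k / N.

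Showing these children as a missing category under SAP 5.1.2, instead of as non-responders, leaves the percentage at x / N, since they stay in the denominator.

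**Case A: N = 66, no discontinuations, 3 children truly unsuppressed and all 3 sampled (63/66 = 95.5% suppressed).** Then x = 66 − 3 − k. Intervals are Clopper-Pearson 95%.

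| k | SAP wording | Observed cases |
|---|---|---|
| 3 | 60/66 = 90.9% (81.3–96.6) | 60/63 = 95.2% (86.7–99.0) |
| 5 | 58/66 = 87.9% (77.5–94.6) | 58/61 = 95.1% (86.3–99.0) |
| 7 | 56/66 = 84.8% (73.9–92.5) | 56/59 = 94.9% (85.9–98.9) |
| 13 | 50/66 = 75.8% (63.6–85.5) | 50/53 = 94.3% (84.3–98.8) |

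At k = 4 the SAP figure is 59/66 = 89.4% (79.4–95.6). The interval therefore first excludes 95% at k = 5.

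**Case B: N = 62, p = 93%.** The 93% is borrowed from the Month 6 LH assumption, because no sex steroid rate is given.

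| k | SAP wording | Observed cases | Expected shortfall |
|---|---|---|---|
| 3 | 55/62 = 88.7% (78.1–95.3) | 55/59 = 93.2% (83.5–98.1) | 0.93 × 3/62 = 4.5 points |
| 5 | 53/62 = 85.5% (74.2–93.1) | 53/57 = 93.0% (83.0–98.1) | 0.93 × 5/62 = 7.5 points |
| 10 | 48/62 = 77.4% (65.0–87.1) | 48/52 = 92.3% (81.5–97.9) | 0.93 × 10/62 = 15.0 points |

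**Male column.** SAP 5.1.1.1 presents every summary table by sex. With the minimum of three boys, one such visit caps the male rate at 2/3 = 66.7%.

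**The case against.** **Whether a sample is lost.** Appendix 7 lists what the telemedicine visit gathers; it does not say the blood draw is dropped. Protocol 1.3 allows remote assessment and refers to separate guidance. A sample drawn elsewhere and assayed centrally would count. This stands: the absence of a sample is the natural reading of Appendix 7, not an explicit statement.

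**Whether the rule applies.** The only example of non-responder imputation is discontinuation, and these children have not discontinued. That shows what the authors may have had in mind, but the example is offered as an instance of a rule stated for every response definition. If only discontinuation is meant, the SAP needs to say so. Under SAP 5.1.2 alone the children might appear as missing, which makes the cause visible but leaves the percentage just as low.

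**Whether a reader would be misled.** The SAP also plans Month 9 summaries of change in sex steroids and of basal LH and FSH, each with n and with no imputation rule, plus plots by visit, an efficacy listing and a listing of COVID-19 deviations. These would partly reveal the cause. A reader might infer that a Month 9 dip with recovery at Month 12 would pass as loss of suppression after the second dose. The documents support that only if the one row is read in isolation. Recovery is not assured either, since Appendix 7 also allows withdrawal at other visits.

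**Stakes.** This is one time point of one untested secondary endpoint, and the imputation works against the sponsor. That argues for keeping the imputed figure and adding to it. It does not justify leaving the ambiguity in place. The per-protocol option in Protocol 9.3 would not help: exclusion there depends on deviations that could affect the Month 6 primary endpoint.

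**Conclusion.** The point holds as a conditional one. If a continuing child has a telemedicine Month 9 visit and no centrally assayed sample results, the SAP as worded biases the Month 9 sex steroid proportion downward whenever that child was in fact suppressed: by 1.5 points per child at N = 66, or 1.6 at N = 62. For an assumed 3 to 13 such visits and about 95% suppression at N = 66, the reported rate is 90.9% to 75.8%, against 95.2% to 94.3% observed. Treating the observed-case rate as the reference further assumes that pandemic access is unrelated to hormone suppression.

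Two stronger readings are tempting and not supported. One is that the protocol cancels the blood draw, so that a false fall is certain. Appendix 7 is silent on the draw, remote collection is left to a document not available here, and at least one such visit must occur. The other is that the trial's efficacy conclusion is at risk. The primary endpoint is Month 6 LH, and its test and power are untouched; the Month 9 LH and FSH summaries carry no imputation rule.

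**What to change.** **SAP 5.7.1.2.** State that non-responder imputation applies to children who discontinued. For children still in the study whose Month 9 sample is missing because of a COVID-19 adapted visit, report the Month 9 sex steroid proportion on observed cases, with its n, the number missing and the exact interval, next to the non-responder figure and not in place of it. The children can be identified, because Protocol 1.3 and Appendix 7 already require adapted visits to be recorded as protocol deviations. The same sentence should say how any other missed or failed sample in a continuing child is handled.

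**Protocol.** Reconcile section 1.3 with Appendix 7 on which visits may be remote and on whether a blood sample is expected when one is.

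**Cost.** One SAP sentence, one extra row in one secondary table and a protocol clarification. The observed-case figure has a slightly smaller denominator and, for a given proportion, a wider interval.

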- p **Clinical laboratory** tests including chemistry, haematology and urinalysis. In case of abnormal blood glucose as per investigator's judgement, repetition of these tests will be performed before the injection and fasting status might be required.
- q **Physical examination and vital signs** blood pressure and heart rate.
- r **Prior and concomitant medications** assessed at every visit
- s **Study drug administration** following all other assessments, apart from PK samples on Day 1 and Month 6
- t **Local tolerability** Measured by tenderness, redness, bruising, erythema, swelling, rash, pain, itching, induration, haematoma, ulceration or necrosis, immediately and 2 hours after triptorelin injection.
- u **EOS/Early Withdrawal** For participants who do not have a final visit within 6 months after their last triptorelin dose, efficacy evaluations (including PK sampling) will not be performed. Data from any efficacy evaluations performed after this time will not be collected on the eCRF.
- v **BMI** will not be collected at Month 9.
- w If the screening tests performed within 1 week prior to Day 1, clinical laboratory assessment will not be repeated on Day 1.

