2.1 Study Rationale

Currently marketed in China there is a triptorelin 1-month formulation indicated for the treatment of children with CPP.

A global pivotal study, DEBIO 8206-CPP-301, demonstrated the efficacy and safety of the 6-month formulation over a period of 12 months and led to registration in the EU and USA.

This current study is intended to document the efficacy, safety and PK of triptorelin 6-month formulation in Chinese children with CPP over a period of 12 months.

Henceforth in this protocol, triptorelin pamoate 22.5 mg 6-month formulation will be referred to as 'triptorelin 6-month formulation'.

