6.8 Concomitant Therapy

Any medication or vaccine (including over the counter or prescription medicines, recreational drugs, vitamins, and/or herbal supplements) that the participant receives within 2 months before triptorelin administration or during triptorelin administration must be recorded on the eCRF along with:

- Generic or trade name
- Reason for use
- Dates of administration including start and end dates
- Dosage information including dose and frequency

The medical monitor should be contacted if there are any questions regarding concomitant or prior therapy.

The following concomitant medications are not permitted during this study:

- Any treatment or procedure with an effect on the metabolism or secretion of gonadotropins (LH or FSH) or sex steroids (oestradiol and/or testosterone) will be considered as a protocol violation
- All drugs mentioned as prohibited in the non-inclusion criteria remain prohibited during the study period: GnRH analogues (other than triptorelin 6-month formulation), medroxyprogesterone acetate, growth hormone or IGF-1, systemic or inhaled steroids (mild topical steroids are permitted) or anticoagulants.

- Drugs which raise prolactin levels should not be prescribed concomitantly as they reduce the level of GnRH receptors in the pituitary. When triptorelin is co-administered with drugs affecting pituitary secretion of gonadotropins, caution should be taken, and it is recommended that the participant's hormonal status be supervised.

6.8.1 *Rescue Medicine*

Not applicable

Approved

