7 DISCONTINUATION OF STUDY INTERVENTION AND PARTICIPANT DISCONTINUATION/WITHDRAWAL

7.1 Discontinuation of the Study Intervention

In rare instances, it may be necessary for a participant to permanently discontinue study intervention. If study intervention is permanently discontinued, the participant will remain in the study to be evaluated for efficacy, safety and PK, with assessments described in the SoA. See the SoA for data to be collected at the time of discontinuation of study intervention and follow-up and for any further evaluations that need to be completed.

7.1.1 *Pregnancy*

See Section 8.3.5.

7.1.2 *Temporary Discontinuation*

In case of suspected or confirmed COVID-19 (SARS-CoV-2) infection, the intervention administration may be temporarily discontinued depending on the participant clinical presentation. In some cases, the investigator may request a participant be retested before the intervention administration is resumed.

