2.1.3 Hypotheses

The null hypothesis H0: $P \leq 80\%$ versus the alternative hypothesis H1: $P > 80\%$, where P is the proportion of children with LH suppression defined as stimulated peak LH ≤ 5 IU/L after

GnRH stimulation at Month 6.

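### A child who has a prohibited GnRH analogue before the Month 6 test, stays in the study and has peak LH ≤5 IU/L counts as a success of the 6-month formulation

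*SAP*

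**What the plan says.** **Endpoint and set.** SAP 2.1.3 tests P ≤ 80% against P > 80%, "where P is the proportion of children with LH suppression defined as stimulated peak LH" ≤5 IU/L after GnRH stimulation at Month 6. SAP 5.7.2.1 adds no condition on other treatment. The primary set (SAP 4, ITT) is everyone who received at least one dose.

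**Non-response.** SAP 5.7.1.2, on dropouts and missing data, applies non-responder imputation to all definitions of response. Its one example is that "participants who discontinue before evaluation of the endpoint (Month 3, Month 6, Month 9 and Month 12) will be declared non-responder".

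**Prohibited treatment.** Protocol 6.8 keeps several drugs off limits during the study, among them "GnRH analogues (other than triptorelin 6-month formulation), medroxyprogesterone acetate, growth hormone or IGF-1". It classes any treatment that affects gonadotropins or sex steroids as a protocol violation and gives no consequence for the analysis. SAP 5.5 provides a listing of prohibited medication.

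**Staying in the study.** Protocol 7.1 says: "If study intervention is permanently discontinued, the participant will remain in the study to be evaluated for efficacy, safety and PK". The withdrawal reasons in Protocol 7.2 include lack of efficacy but not prohibited medication.

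**Other analyses.** SAP 5.7.2.3 repeats the analysis on the mITT and per-protocol sets. The per-protocol set leaves out mITT children with major deviations that could affect the primary endpoint, as classified under a separate deviation plan (SAP 5.3). SAP 5.7.2.4 plans no supplementary analysis. The SAP abbreviates intercurrent event and cites ICH E9(R1), but sets no strategy for any such event.

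**The concern.** This is a single-arm comparison with a fixed 80%. If another GnRH analogue produces the suppressed LH at Month 6, the result is credited to the 6-month formulation, and there is no control arm in which the same thing could happen. The omission can only add successes, because the missing rule could only take them away.

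The event is conceivable. Protocol 2.1 notes: "Currently marketed in China there is a triptorelin 1-month formulation indicated for the treatment of children with CPP". A child whose Month 3 stimulation test shows poor suppression is an obvious candidate for another product, so the children affected would tend to be those in whom the study drug was not working. At stake is whether the primary proportion measures suppression by the study product or suppression by whatever the child received.

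**Working it through.** **1. The plan's own figure.** Inputs from SAP 2.3: "Null proportion is 80"%; expected proportion "at Month 6 is 93"%; exact binomial test, one-sided 0.025; power 85%; dropout 5%. The success threshold r is the smallest count with P(X ≥ r | n, 0.80) ≤ 0.025.

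- n = 62: r = 56, P(X ≥ 56 | 0.80) = 0.0238, power P(X ≥ 56 | 0.93) = 0.858.
- Enrolment: 62 / (1 − 0.05) = 65.3, rounded up to 66.

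The stated 62 treated and 66 enrolled are reproduced. If all 66 are dosed and so in the ITT set, r = 60 and P(X ≥ 60 | 0.80) = 0.0139.

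**2. Following one child through the rules.** Suppose a child is dosed on Day 1, receives a prohibited analogue before Month 6, attends, and has peak LH ≤5 IU/L.

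| Rule | Effect on this child |
|---|---|
| ITT (SAP 4) | Included |
| Response definition (SAP 5.7.2.1) | Met |
| Non-responder imputation (SAP 5.7.1.2) | Nothing to impute; the value is observed |
| Protocol 6.8 | Protocol violation |
| Prohibited-medication listing (SAP 5.5) | Listed |
| mITT sensitivity analysis | Included as a success |
| Per-protocol sensitivity analysis | Removed if the deviation is classed as major and relevant to the endpoint |

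No rule scores the child as a failure.

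**3. Effect on the test.** If k successes are recoded as failures, x/n becomes (x − k)/n:

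| Observed | k | After recoding | One-sided p | Clopper-Pearson lower limit | Above 80%? |
|---|---|---|---|---|---|
| 56/62 | 0 | 56/62 | 0.0238 | 80.1% | yes |
| 56/62 | 1 | 55/62 | 0.0532 | 78.1% | no |
| 58/62 | 2 | 56/62 | 0.0238 | 80.1% | yes |
| 58/62 | 3 | 55/62 | 0.0532 | 78.1% | no |
| 60/66 | 0 | 60/66 | 0.0139 | 81.3% | yes |
| 60/66 | 1 | 59/66 | 0.0330 | 79.4% | no |
| 62/66 | 2 | 60/66 | 0.0139 | 81.3% | yes |
| 62/66 | 3 | 59/66 | 0.0330 | 79.4% | no |

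The planned 93% corresponds to about 58 of 62 (93.5%).

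**4. Why the per-protocol set is not a substitute.** Take 58/62 with three such children and no other exclusions. Per protocol this becomes (58 − 3)/(62 − 3) = 55/59, which passes because 54 are needed at n = 59 (P(X ≥ 54 | 0.80) = 0.0140). Scoring the three as failures gives 55/62, p = 0.053, which does not pass.

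**5. False-positive rate (illustration).** Assume that the study drug alone suppresses 80% and that a further m% of all children are suppressed through a prohibited analogue and counted. The documents give no value for m.

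| m | n = 62 | n = 66 |
|---|---|---|
| 0 | 2.4% | 1.4% |
| 1 | 3.6% | 2.2% |
| 2 | 5.4% | 3.5% |
| 3 | 8.0% | 5.3% |

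At n = 62, m = 2 corresponds to 0.02 × 62 = 1.2 children on average.

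**The case against.** **The event should be rare.** Other analogues are banned, Protocol 6.8.1 gives rescue medicine as not applicable, and Protocol 8 allows no waivers. Lack of efficacy is a listed withdrawal reason, and a child withdrawn for it before Month 6 is a non-responder. The gap needs a site to breach 6.8 and keep the child in the study, and the child then to be suppressed at Month 6. This stands: nothing in the documents suggests that such cases are expected.

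**They would be visible.** The prohibited-medication listing, the deviation tables and listings, and the per-protocol analysis would make one or two such children identifiable in a trial of this size. This also stands, but a listing does not change the primary count, and step 4 shows the limit of the per-protocol set.

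**Discontinuation might include stopping study treatment.** The SAP does not say so, and that reading would not close the gap. By footnotes a and s of the Schedule of Activities, the Month 6 test precedes the second injection. A child given another analogue between Day 1 and Month 6 has missed no scheduled study dose.

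**ITT means counting what was observed.** That is a legitimate strategy if it is stated and justified. The plan does neither, and against a fixed threshold it answers a question about any treatment received.

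**Stronger readings to avoid.** A reader might infer that the imputation reaches discontinued children only. The SAP offers discontinuation as an example, so other missing values can be covered. A reader might also infer from the Schedule of Activities that a child moved to monthly triptorelin could be tested at Month 12 and counted, because footnote u says: "For participants who do not have a final visit within 6 months after their last triptorelin dose, efficacy evaluations (including PK sampling) will not be" carried out. The protocol uses plain triptorelin for the study product throughout, and that is the natural meaning here. On that meaning, a child with only the Day 1 injection is past the limit by Day 337, so the value is missing and imputed as non-response.

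**Conclusion.** The point holds for the primary ITT analysis and, by the same logic, for the mITT analysis. An observed peak LH ≤5 IU/L after a prohibited gonadotropin-suppressing treatment is counted as a success, and no rule in either document makes it a failure.

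The size is conditional. The number of such children is not given and may be zero. One child changes the conclusion only if the count is exactly at the threshold (56/62 or 60/66); near the planned rate it takes three. It would be tempting to say that the type I error is inflated. The documents do not support that as a finding, because the rates in step 5 are assumptions. They show only that about one child on average would be enough to pass 2.5% at n = 62.

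This is a gap in the rules of the primary analysis that is cheap to close. It is not evidence that the result will be wrong.

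**What to change.** Change the SAP only. Add to 5.7.1.2, and refer to it in 5.7.2.2:

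*A participant who, on or after Day 1 and before the assessment, received any GnRH analogue other than the study formulation, or another treatment prohibited in Protocol 6.8 for its suppressive effect on gonadotropins or sex steroids (including medroxyprogesterone acetate), is a non-responder at that and all later visits for LH suppression, including maintenance from Month 6 to Month 12, and for prepubertal sex steroids. The gonadorelin given for the stimulation test does not count as such use.*

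Fix the list of qualifying drugs before database lock, without reference to the children's LH values.

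**Cost.** A short addition to the SAP. Protocol 6.8 already requires medication start and end dates on the eCRF. Sample size, visits and clinical management do not change, and footnote u needs no edit. The downside is that the reported response rate may be slightly lower, since a child whom the study drug would have suppressed anyway is also scored as a failure.
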